10. TREATMENT DOSAGE AND ADMINISTRATION

Patients who are on ruxolitinib will continue their current dose. Patients who are not on ruxolitinib will receive ruxolitinib per Table 1 dosing based on platelet count (modified package insert dosing). Enasidenib will be given at 100 mg daily on enrollment for patients with accelerated and blast phase myelofibrosis regardless of platelet count (this will be deemed Cycle 1). Patients with chronic phase myelofibrosis will receive Enasidenib at starting dose of 50 mg daily for cycle 1. The dose of Enasidenib will be increased to 100 mg for cycle 2 if the platelet count stays above 50,000 at the end of cycle 1 (Table 3a) and no other therapy emergent SAE of grade \geq 2 developed (except grade 2 hyperbilirubinemia that is acceptable for dose escalation).

Ruxolitinib and enasidenib will be given orally in an outpatient setting unless the patient is being seen inpatient for another reason. Ruxolitinib and enasidenib will be given orally in 28-day cycles.

Patients should fast 2 hours before and 1-hour post enasidenib. Ruxolitinib may be administered independent of fasting and may be given with enasidenib. All protocol mandated visits will be performed at one of the participating institutions. Patients will return to the treating institution at a minimum of weekly during Cycles 1 and 2, every 4 weeks for Cycles 3 and beyond. Additional clinic visits will be mandated according to the patient clinical condition and at the discretion of the treating provider. Patients will have an end of study visit for a safety follow-up at 30 days after their last dose of therapy.

The dosages of ruxolitinib and/or enasidenib can be reduced, based on assessment of adverse events, if any occur, as described below in Section 10.1. Missed or vomited doses of ruxolitinib or enasidenib will not be made up.

Twenty-eight days is considered one cycle of therapy. Attempts will be made to provide an adequate treatment period with the combination of at least 6 cycles, unless significant toxicity is observed, to account for delayed time to response observed with biologic agents. Responders will continue therapy indefinitely unless progression of disease occurs, toxicity warranting discontinuation of therapy is

A Phase II Open-label Study of Combined Ruxolitinib and Enasidenib Sinai in Patients with Accelerated/Blast-phase Myeloproliferative Neoplasm or Chronic-

phase Myelofibrosis with an IDH2 Mutation

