12.0 STUDY TIMELINES

Baseline evaluations are to be conducted within 30 days of the first study drug administration, unless otherwise indicated within the Schedule of Assessments outlined in **Table 4**. All scheduled visits will have a ± 7 days window unless otherwise stated or indicated within the Schedule of Assessments outlined below.

Ruxolitinib and enasidenib will be given orally in 28- day cycles. Attempts will be made to provide an adequate treatment period with the combination of at least 6 cycles, unless significant toxicity is observed, to account for delayed time to response observed with biologic agents. Interval Milestone Response Assessment (IMRA) can be performed at the beginning of any cycle after cycle 1 if specific milestones are achieved that will prompt such an evaluation. Specific milestones that will prompt assessment consist of clearance of blasts from peripheral blood in accelerated/blast phase patients, which will prompt bone marrow aspirate and biopsy. In addition progression of disease (as determined by an increase in blasts in the peripheral blood - defined as doubling of blasts % and achieving more than 10% in the chronic phase patients at least 7 days apart) will prompt IMRA. Responders will continue therapy indefinitely unless progression of disease occurs, toxicity warranting discontinuation of therapy is observed, or at the discretion of the treating physician. Patients will have an end of study visit for a safety follow-up at 30 days after their last dose of therapy.

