13.0 STUDY ENDPOINTS

13.1 PRIMARY ENDPOINT

• The proportion of treated accelerated-phase and blast-phase MPN patients (primary cohort) that achieve a best response of either complete response (CR), Partial Response (PR), or complete response with incomplete recovery of counts (CRi), when treated with the combination of ruxolitinib with enasidenib within 6 cycles of combined therapy.

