15. TREATMENT PERIOD

The subject must be enrolled into the study, at the latest 30 days from signing the ICF, following Sponsor review of eligibility. The Treatment Period begins at Cycle 1 Day 1 and ends at the End-of-Treatment Visit. During the Treatment Period, all subjects will be closely monitored for safety. Toxicities (AEs and laboratory abnormalities) will be evaluated and graded according to the CTCAE. During this period the following assessments should occur:

- Bone marrow biopsy and aspirate with cytogenetics and molecular genetic profiling for presence of JAK2 (or MPL or CALR mutation status in the case that no JAK2 mutation is detected) as well as IDH2 mutation status. This is done at C4 D1 (for all accelerated patients, may be done at the discretion of the Investigator for chronic phase patients), C7 D1 (for all patients), C10 D1(for accelerated phase patients, may be done at the discretion of the Investigator for chronic phase patients), and every 6 cycles, thereafter (for all patients).
- Transfusion history will be collected on Day of each cycle
- Pregnancy Test
- A physical exam including a review of current medical conditions and medications
- Vital signs (heart rate, breathing rate, blood pressure, temperature, weight, and height)
- ECOG performance status
- Adverse events and concomitant medications
- Complete blood counts and serum chemistry
- Spleen volume assessment by CT/MRI at C7 D1, and C10 D1
- ECG, day 1 of each cycle until Cycle 7
- Research blood sample collection
- MF-SAFv4.0 questionnaire (paper or electronic)
- Enasidenib administration
- Medication diary collected and new one dispensed

in Patients with Accelerated/Blast-phase Myeloproliferative Neoplasm or Chronicphase Myelofibrosis with an IDH2 Mutation

(Myeloproliferative Neoplasms Research Consortium [MPN-RC] 119)

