20.1 ACCELERATED / BLAST-PHASE COHORT

Primary endpoint: The primary endpoint of this study is best overall response, defined as partial response or better (CR+PR+Cri), and will be defined as the best response within 6 cyclesof combination therapy. All patients meeting the eligibility criteria who have signed a consent form and have begun treatment will be evaluable for response. Any evaluable patient not meeting the definition for response will be deemed as having a non-response.

Design: The largest overall response rate where the proposed combination treatment regimen would be considered ineffective in this patient population is 5%, and the smallest response rate that would warrant subsequent studies with the proposed regimen is 25%. This is based on retrospective analysis applying the 2013 IWG Response Criteria to patients treated with ruxolitinib¹. A Simon's two-stage minimax design will be employed to test the null hypothesis that the true overall response rate in this patient population is at most 5%.

Decision Rule: Enter 13 patients into the study. If 0 responses are observed in the first 13 patients (Stage 1), we may consider this regimen ineffective in the patient population and the trial will close due to a lack of efficacy. If 1 or more responses are observed in the first 13 evaluable patients, we will proceed to Stage 2 and enroll an additional 7 patients onto the study for a total of 20 patients. After completion of both stages, if 3 or more responses out of the 20 patients are observed, the combination therapy will be considered promising for further investigation.

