21. SAMPLE SIZE AND ACCRUAL

The maximum sample size in the Phase II (accelerated/blast-phase) is 20 evaluable patients. Allowing for enrollment of up to 2 additional patients as replacements for unevaluable patients (ineligibility, cancellation, major treatment violation, or other reasons), this study will enroll a maximum of 22 patients in the Phase II AP/BP cohort. The maximum sample size in the chronic phase MPN is 9 evaluable patients. Allowing for enrollment of up to 1 additional patient as replacement for unevaluable patients, this study will enroll a maximum of 10 patients in the descriptive chronic phase MPN cohort. Therefore, a maximum total of 32 (22 + 10) patients will be enrolled in the trial.

The anticipated accrual rate is approximately 2-3 patients per month. Therefore, the accrual period for this study is expected to be 15 months. The primary analysis can begin approximately 21 months after the trial begins, i.e., as soon as the last patient has been observed for 6 cycles.

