22. DATA ANALYSIS PLANS

22.1 PRIMARY ENDPOINT

Overall response rate (ORR): The overall response rate will be estimated by the number of patients that attain a response (defined above per cohort) by 6 cycles of combination therapy divided by the total number of treated eligible patients. A two-sided 95% confidence interval for the true overall response rate will be calculated according the exact binomial method.

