34.1 APPENDIX A: RESPONSE CRITERIA

Complete Response	As per 2013 IWG-MRT and ELN Criteria
Partial Response	As per 2013 IWG-MRT and ELN Criteria
Clinical Improvement (CI)	As per 2013 IWG-MRT and ELN Criteria
Anemia Response	As per 2013 IWG-MRT and ELN Criteria
Spleen Response	As per 2013 IWG-MRT and ELN Criteria
Symptom Response	As per 2013 IWG-MRT and ELN Criteria
Progressive Disease	 After at least 3 cycles of combined therapy: New splenomegaly that is palpable at least 5cm below the LCM a ≥100% increase in palpable distance, below LCM, for baseline splenomegaly of 5-10cm or a 50% increase in palpable distance, below LCM, for baseline splenomegaly of > 10cm Progression from chronic-phase disease (< 10% blasts) to blast-phase (≥ 20% blasts) disease on two separate CBCs within 28 days For patients in accelerated of blast phase disease at baseline, a doubling of the absolute blast count
Stable Disease	As per 2013 IWG-MRT and ELN Criteria
Cytogenetic Remission	As per 2013 IWG-MRT and ELN Criteria
Molecular Remission	 Complete Molecular remission: eradication of IDH2 and JAK2/MPL/CALR mutations as assessed by both next-generation sequencing and digital PCR assays. Partial Molecular remission: 50% reduction in mutant IDH2 and JAK2/MPL/CALR allele burden as assessed by next-generation sequencing
Cytogenetic/Molecular Relapse	As per 2013 IWG-MRT and ELN Criteria
Complete Blast Response	Absence of circulating peripheral blood blast count with residual features of chronic-phase MPN maintained for at least 28 consecutive days.
Partial Blast Response	Reduction to <4% blast count in peripheral blood with residual features of chronic-phase MPN maintained for at least 28 consecutive days.

A Phase II Open-label Study of Combined Ruxolitinib and Enasidenib Sinai in Patients with Accelerated/Blast-phase Myeloproliferative Neoplasm or Chronic-

phase Myelofibrosis with an IDH2 Mutation

(Myeloproliferative Neoplasms Research Consortium [MPN-RC] 119)

34.2 **APPENDIX B: IWG-MRT AND ELN RESPONSE CRITERIA**

Response categories	Required criteria (for all response categories, benefit must last for ≥12 wk to qualify as a response)
CR	Bone marrow:*Age-adjusted normocellularity; <5% blasts; ≤grade 1 MF† and
	Peripheral blood: Hemoglobin \geq 100 g/L and <unl; <math="" count="" neutrophil="">\geq 1 \times 10⁹/L and <unl;< td=""></unl;<></unl;>
	Platelet count \geq 100 \times 10 ⁹ /L and $<$ UNL; <2% immature myeloid cells‡ and

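### Does the 12-week duration built into CR and PR conflict with a six-cycle primary endpoint analysed at about month 21?

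*Combined protocol and SAP*

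**What the plan says.** Appendix A takes CR and PR from the 2013 IWG-MRT/ELN criteria unchanged. The Appendix B table of those criteria carries the condition "for all response categories, benefit must last for ≥12 wk to qualify as a response". Complete and partial blast response, which are secondary, have their own 28-day rule in Appendix A.

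Section 13.1 counts CR, PR or CRi "when treated with the combination of ruxolitinib with enasidenib within 6 cycles of combined therapy". Section 22.1 divides the number attaining a response "by 6 cycles of combination therapy divided by the total number of treated eligible patients". Section 20.1 adds: "Any evaluable patient not meeting the definition for response will be deemed as having a non-response". The design stops after 0 responses in 13 and is promising at 3 or more in 20.

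Section 21 expects 15 months of accrual and lets the primary analysis begin at approximately month 21, "as soon as the last patient has been observed for 6 cycles".

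For assessments, Section 15 schedules an on-treatment marrow early: "This is done at C4 D1 (for all accelerated patients". Table 4 footnote 6 makes that marrow discretionary only for chronic-phase patients, and further marrows follow at C7D1 and C10D1. Section 12 and Table 4 footnote 13 allow an interval response assessment at the start of any cycle after cycle 1 when a milestone is met. Table 4 footnote 9 places the regular response assessment after six cycles.

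**The concern.** A response with a minimum duration has two dates, onset and qualification, and the plan does not say which must fall within six cycles.

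- **Qualification inside the window.** Onset must come by about C4D1. A response first found at the regular post-cycle-6 assessment could then never count, which sits awkwardly with Section 10's reason for giving at least six cycles: "to account for delayed time to response observed with biologic agents".
- **Onset inside the window, duration confirmed later.** A response first found at C7D1 needs follow-up to C10D1. An analysis at month 21 could then score late-enrolled patients as non-responders for lack of follow-up, while identical earlier patients counted as responders.

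With thresholds of 0/13 and 3/20, one reclassified patient can change a decision, so it is natural to ask whether the design or its timetable is broken.

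**Working it through.** **1. Reproduce the plan's figures.** Inputs (Sections 20.1 and 21): stop at 0/13, success at ≥3/20, 15 months of accrual, 28-day cycles; 4.348 weeks per month.

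- Exact binomial at p = 0.25: early stop 0.75^13 = 0.024, power 0.903. At p = 0.05: early stop 0.95^13 = 0.513, type I error 0.074. These agree with Table 6.
- Analysis date: 6 × 28 = 168 days = 5.52 months; 15 + 5.52 = 20.5, or 15 + 6 calendar months = 21. The stated figure reproduces, and it contains no allowance for confirmation after cycle 6.

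**2. Reading A: the 12 weeks end by cycle 6.** Latest onset is day 168 − 84 = 84, which is C4D1. The AP/BP marrow falls there, counts and spleen and liver measurement are scheduled on day 1 of each cycle, and C7D1 closes the interval. "All scheduled visits will have a ± 7 days window", so the nominal 84 days can be 70 to 98, and analysts need an ordinary visit tolerance. Section 20.1 bases the 5% and 25% on the 2013 criteria, so they are naturally read as rates of qualifying responses. On that reading Table 6 applies as it stands and no power is lost.

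**3. Reading B: the 12 weeks may end after cycle 6.** A C7D1 response is confirmed at day 168 + 84 = 252 = 8.28 months, at C10D1. For a patient starting at month 15 this is 15 + 8.28 = month 23.3.

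Patients without 36 weeks at month 21 are those starting after 21 − 8.28 = month 12.72. With uniform AP/BP accrual over 15 months (an assumption), this is (15 − 12.72)/15 × 20 = 3.0 patients. At the literal trigger (month 20.5) it is 2.76/15 × 20 = 3.7.

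Let s be the share of responders first found at C7D1. The documents give no value, so a range is shown. The last k Stage 2 patients then have response rate p(1 − s):

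| s | Power, k = 3 | Type I error, k = 3 | Power, k = 4 |
|---|---|---|---|
| 0.1 | 0.897 | 0.071 | 0.895 |
| 0.2 | 0.891 | 0.069 | 0.887 |
| 0.3 | 0.885 | 0.066 | 0.879 |
| 0.5 | 0.872 | 0.062 | 0.860 |

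These losses arise only if Reading B is adopted and the analysis is still run without waiting.

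**4. Stage 1 under Reading B.** When the 13th patient reaches C7D1, anyone enrolled at least 12 weeks earlier has already reached C10D1. AP/BP accrual in 12 weeks (2.76 months) is 2 × 22/32 × 2.76 = 3.8 to 3 × 22/32 × 2.76 = 5.7, so only about the last 4 to 6 of 13 can be pending. The chance that responders exist but all are pending is (1 − p)^(13 − k) × [(1 − p(1 − s))^k − (1 − p)^k]. At p = 0.25 and s = 0.1/0.2/0.3/0.5:

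- k = 4: 0.3/0.7/1.1/2.0%
- k = 6: 0.5/1.1/1.8/3.6%

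Treating all 13 as pending would give 1.3% to about 15%, which overstates the exposure.

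**5. Cost of fixing C10D1 confirmation as the rule.** Readout moves from month 21 to about 24, or to 23.3 + 2.8 = about 26 if accrual pauses at Stage 1. C7D1 to C10D1 has the same 70-to-98-day spread, so a strict 84-day requirement at C10D1 could itself fail in some patients.

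**The case for a change.** The best case for a change does not rest on average power. The duration rule looks deliberate, since the sponsor wrote a different one for blast response. The trial is open-label and single-arm, so an unwritten choice between the two readings could be made with results in view, and one patient can decide 3/20 or 0/13. Late onset is plausible: Section 6.3 reports a median of 1.9 months (8.3 weeks) to first response and 3.7 months (16.1 weeks) to best response, either side of week 12.

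Part of this stands. The rule is unwritten, a patient first in response at C7D1 is classified differently under the two readings, and the in-window reading does exclude late responses.

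The rest is weaker. The text is not neutral: a response that must last 12 weeks to qualify, attained by six cycles and analysed after six cycles of observation, is one that has qualified by then. The post-cycle-6 assessment still has uses on that reading, because it closes the 12-week interval and, in the Section 3 schema, informs continuation of treatment.

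Nor need detection wait for C7D1. Blast clearance from blood prompts a marrow under Section 12. CR and PR both require under 2% immature myeloid cells, a count that includes blasts, so many responders should be assessed earlier. Table 4 footnote 7 lets the physician omit a marrow but still asks for one to confirm complete response. The Section 6.3 medians come from relapsed or refractory AML on enasidenib alone under other criteria, so they do not fix the late share here.

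**Conclusion.** The plan leaves a rule unwritten, but analysts can fill the gap sensibly and neither way of doing so breaks the design. The favoured reading, qualification by the end of cycle 6, is consistent with the endpoint, the analysis trigger and the visit schedule, and it leaves Table 6 intact if the 5% and 25% are rates of qualifying responses. Under the other reading the Section 21 date is approximate and permissive, so the analysis can wait until about month 23.3. If it did not wait, power at 25% would be 0.897 to 0.872 instead of 0.903 and type I error 0.071 to 0.062 instead of 0.074, so the distortion is conservative. Stage 1 exposure would be about 0.3 to 3.6%.

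These sizes assume uniform AP/BP accrual over 15 months and a late-documented share of 10 to 50%. Section 21 gives the 15 months for both cohorts together, so if AP/BP fills sooner, fewer patients are affected, possibly none. Mandating confirmation at C10D1 would buy at most about 0.03 of power (0.903 − 0.872, k = 3) for a readout about 3 to 5 months later, which is a trade-off and not a correction. CRi is in the primary endpoint but has no entry in Appendix A or B; that is a separate question and does not alter this conclusion.

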34.5 APPENDIX E: EASTERN COOPERATIVE ONCOLOGY GROUP (ECOG) PERFORMANCE SCORE RATINGS

At each clinic visit after the screening visit, the investigator will assess each subject's ECOG performance status according to the following scale:

- 0 Fully active, able to carry on all pre-disease performance without restriction
- 1 Restricted in physically strenuous activity but ambulatory and able to carry out work of a light or sedentary nature, e.g., light house-work, office work
- 2 Ambulatory and capable of all self-care but unable to carry out any work activities. Up and about more than 50% of waking hours
- 3 Capable of only limited self-care, confined to bed or chair more than 50% of waking hours
- 4 Completely disabled. Cannot carry on any self-care. Totally confined to bed or chair
- 5 Dead

A Phase II Open-label Study of Combined Ruxolitinib and Enasidenib Sinai MPN-RC in Patients with Accelerated/Blast-phase Myeloproliferative Neoplasm or Chronicphase Myelofibrosis with an IDH2 Mutation (Myeloproliferative Neoplasms Research Consortium [MPN-RC] 119) 34.6 APPENDIX F: MYELOFIBROSIS SYMPTOM ASSESSMENT FORM (MF-SAF) V4.0 Instructions: The following questions refer to symptoms that you may experience as a result of your myelofibrosis. Please read through and complete the questions below. There are no right or wrong answers. Please select the answer that best applies to you. 1. During the past 7 days, how severe was your worst fatigue (weariness, tiredness)? Absent Worst Imaginable 2. During the past 7 days, how severe were your worst night sweats (or feeling hot or flushed)? Absent Worst Imaginable 3. During the past 7 days, how severe was your worst itching? Absent Worst Imaginable 4. During the past 7 days, how severe was your worst abdominal discomfort (feel pressure or bloating)? Absent Worst Imaginable 5. During the past 7 days, how severe was the worst pain under your ribs on your left side? Absent Worst Imaginable 6. During the past 7 days, what was the worst feeling of fullness you had after beginning to eat? Absent Worst Imaginable 7. During the past 7 days, how severe was your worst bone pain (not joint or arthritis pain)? Absent Worst Imaginable

Confidential

A Phase II Open-label Study of Combined Ruxolitinib and Enasidenib Sinai in Patients with Accelerated/Blast-phase Myeloproliferative Neoplasm or Chronic-

phase Myelofibrosis with an IDH2 Mutation

(Myeloproliferative Neoplasms Research Consortium [MPN-RC] 119)

34.7 APPENDIX G: NEW YORK HEART ASSOCIATION (NYHA) CLASS

III OR IV CONGESTIVE HEART FAILURE

MPN-RC

Class	Patient Symptoms
I(Mild)	No limitation of physical activity. Ordinary physical activity does not cause undue fatigue, palpitation, or dyspnea (shortness of breath).
II(Mild)	Slight limitation of physical activity. Comfortable at rest, but ordinary physical activity results in fatigue, palpitation, or dyspnea.
III(Moderate)	Marked limitation of physical activity. Comfortable at rest, but less-than-ordinary activity causes fatigue, palpitation, or dyspnea.
IV(Severe)	Unable to carry out any physical activity without discomfort. Symptoms of cardiac insufficiency at rest. If any physical activity is undertaken, discomfort is increased.
Source: Dolgin M, Fox AC, Devereaux RB. Nomenclature and criteria for diagnosis of diseases of the heart and great vessels. 9 th ed. Boston: Little Brown and Company: 1994 p.253-256.	

A Phase II Open-label Study of Combined Ruxolitinib and Enasidenib Sinai

in Patients with Accelerated/Blast-phase Myeloproliferative Neoplasm or Chronic-

phase Myelofibrosis with an IDH2 Mutation

(Myeloproliferative Neoplasms Research Consortium [MPN-RC] 119)

34.8 APPENDIX H: FDA MEDWATCH FORM

https://www.fda.gov/downloads/AboutFDA/ReportsManualsForms/Forms/UCM048334.pdf
